4.3. Justification for dose

The VH4004280 and VH4011499 doses for investigation in this study are defined by emerging PK and safety data from the ongoing oral Phase 1 studies, preclinical potency data [RPS-CLIN-048482; RPS-CLIN-026329; RPS-CLIN-047476; RPS-CLIN-046304; RPS-CLIN-056829; RPS-CLIN-056826; TMF-14580566; TMF-14086139; TMF-14580566], and CCI [REDACTED]

A therapeutic dose for VH4004280 and VH4011499 is proposed where majority of participants maintain, concentrations CCI [REDACTED]

[REDACTED], that are expected to provide exposures that result in a near maximal change from baseline in plasma HIV-1 RNA by Day 11.

Thus, VH4004280 and VH4011499 doses in the current study aim to provide the following exposures through the 10-days monotherapy period:

- CCI [REDACTED] aimed to characterize the near maximal decline in HIV-1 RNA.
- CCI [REDACTED] aimed to characterize the near maximal decline in HIV-1 RNA.
- Based on the interim analysis of exposures and response, a dose corresponding to 10-days CCI [REDACTED] [REDACTED] aimed to confirm the maximal decline in HIV-1 RNA.

A population pharmacokinetic (POP PK) analysis was conducted using preliminary data from the ongoing oral Phase 1 studies for VH4004280 and VH4011499 [TMF-15100069; TMF-14909676]. Based on the POP PK analysis, CCI [REDACTED]

[REDACTED] Similarly, using a POP PK analysis for VH4011499, CCI [REDACTED]

Thus, VH4004280 doses for the current study are expected to be CCI [REDACTED]

[REDACTED] for Part 1 and a dose between approximately CCI [REDACTED]

[REDACTED] will be selected for Part 2 based on interim analysis. Similarly, VH4011499 doses for the current study are expected

to be CCI

for Part 1 and a dose between approximately CCI

will be selected for Part 2 based on interim analysis. VH4004280 and VH4011499 doses in Part 2 may be adjusted based on preliminary analyses of exposure and response from Part 1.

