9.4.3.3. Pharmacokinetic-Pharmacodynamic analyses

Analysis Method

The relationship between selected PK parameters (e.g., concentrations on Day 11) and selected PD parameters (e.g., maximum change from baseline in log10 plasma HIV-1 RNA) will be explored graphically. Where relationships are apparent, exposure-response models will be used to characterize the relationship and assess the impact of covariates. The details of such exposure-response analysis will be outlined in a separate CPMS analysis plan and may be presented separately from the main study report. No imputation will be performed for missing data.

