1.1.1. Estimands

Table 1 Estimands Definitions

Endpoints	Estimand			
	Population	Treatment	Summary Measure	Intercurrent event (IE) / strategy / rationale
Primary Objective: To evaluate the antiviral activity of orally administered VH4004280 and VH4011499 monotherapy over 10 days in HIV-1 infected Treatment-Naïve (TN) participants				
Maximum change from baseline (Day 1) in plasma HIV-1 ribonucleic acid (RNA) through Day 11.	Overtly healthy (other than HIV-1 infection) treatment naïve individuals	VH4004280 or placebo single dose on Day 1, or VH4011499 or placebo single dose on Day 1 and Day 6	Mean of maximum change from Baseline in log10 HIV-1 RNA during Days 1-11	
Discontinuation of study treatment due to any reason: Treatment policy strategy, i.e., any HIV-1 RNA data available after study treatment discontinuation day + 1 and prior to starting SoC will be used in calculation of max VLD
 
Use of SoC medication prior to Day 11: While on-treatment strategy, i.e., HIV-1 RNA collected after initiation of SoC, if for any reason this takes place prior to Day 11 will be excluded from calculation of max VLD
 
Use of prohibited medication: Treatment policy strategy, i.e., any HIV-1 RNA data available after use of prohibited medication will be used in calculation of max VLD
 
Missed or incorrect doses of study treatment: Treatment policy strategy, i.e., HIV-1 RNA collected after missed or incorrect dose(s) will be used in calculation of max VLD
 
Rationale: Interest is in evaluating efficacy irrespective of study treatment discontinuation or missed/incorrect doses, or use of prohibited medications, hence a treatment policy strategy is appropriate. Also, interest is to evaluate efficacy of VH4004280/VH4011499 monotherapy and not in combination with

Endpoints	Estimand			
	Population	Treatment	Summary Measure	Intercurrent event (IE) / strategy / rationale
				
other antiretroviral medication hence a while on-treatment strategy is appropriate.
 
Note: discontinuation or missed doses of VH4004280 is not possible as only a single dose on Day 1 is administered, hence these IEs apply only to VH4011499 and to placebo matched for VH4011499.

Secondary Objective: To assess the safety and tolerability of orally administered VH4004280 and VH4011499				

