Concentration on Day 11 and PK parameters including 
 ○ Cmax ○ tmax 	Overtly healthy (other than HIV-1 infection) treatment naïve individuals	VH4004280 or placebo CCI [REDACTED] [REDACTED], or VH4011499 or placebo CCI [REDACTED] [REDACTED] [REDACTED]	Summary statistics (e.g., arithmetic mean, median, std, minimum, maximum, geometric mean, sd (log), %CVb)	
Discontinuation of monotherapy treatment with VH4011499: While on-treatment strategy, i.e., concentration values after study treatment discontinuation day + 1 will be excluded from analysis
 
Use of prohibited medication: treatment policy strategy, i.e., all PK data to be used regardless of whether prohibited medication was used
 
Rationale: Discontinuation of VH4011499 treatment may bias the evaluation of Pharmacokinetic behavior of VH4011499 as expected during and after the end of 10 days monotherapy period
 
Note: discontinuation of VH4004280 treatment is not possible as only a single dose on Day 1 is administered

CCI				

CONFIDENTIAL

218307

Endpoints CCI	Estimand			
	Population	Treatment	Summary Measure	Intercurrent event (IE) / strategy / rationale

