4.3.2.3. Pharmacokinetic Analyses

Pharmacokinetic parameters for VH4004280 and VH4011499 will be calculated by standard non-compartmental analysis according to current working practices and using the currently supported version of WinNonlin. All calculations of non-compartmental parameters for the End of Study analysis will be based on actual sampling times. For the calculation of the Area under the concentration-time curve (AUC), the linear trapezoidal

method will be employed for all incremental trapezoids arising from increasing concentrations and the logarithmic trapezoidal method will be used for those arising from decreasing concentrations (i.e., Linear Up/Log Down calculation method in Phoenix WinNonlin Professional). A minimum number of three data points (not including Cmax) should be used in calculating λz . The pharmacokinetic parameters described in [Table 3](#) will be determined from the plasma concentration-time data, as data permits and they will be included in the final SDTM datasets.

As per the PK Estimand definition in Section [1.1.1](#), in case of discontinuation of VH4011499, only serum concentration data up to the time of discontinuation of VH4011499 will be used in derivation of VH4011499 PK parameters.

Table 3 Definition of PK parameters

Compound	PK Parameter	Definition
VH4004280 & VH4011499	C_{\max}	Maximum observed plasma concentration
VH4004280 & VH4011499	T_{\max}	Time to C_{\max}
VH4004280 & VH4011499	C_{11}	Concentration on Day 11
VH4004280	$AUC_{0-\infty}$	Area under the plasma concentration vs time curve from time zero hours to infinity
VH4011499	AUC_{0-t}	Area under the plasma concentration time curve from time zero to the last quantifiable time point
VH4004280 & VH4011499	AUC_{0-11}	Area under the plasma concentration time curve from time of first dose to Day 11

Note: Additional Parameters may be included as required

At Interim analyses, preliminary PK data will be analysed by CPMS to select appropriate doses for Part 2 of the study.

Summaries of PK concentration values and PK parameters

All pharmacokinetic analyses will be performed on the Pharmacokinetic Analysis Set. For the End of Study analysis, the following apply:

For each compound, pharmacokinetic concentrations collected within the PK analysis visit window (see Section [6.2.4](#)) will be summarised at every scheduled time point using descriptive statistics. PK concentrations sampled outside the PK sampling windows will

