be included in listings and in subject level figures but will not be included in data summaries.

For each compound, derived PK parameters (excluding AUC_{0-11}) will be summarised using descriptive statistics (AUC_{0-11} will be used only for analyses to explore relationship between PK exposure and safety/immunologic endpoints; see Section 4.6.3 and Section 4.6.4).

PK concentrations derived after discontinuation of study treatment will be excluded from PK data summaries, in accordance with the ‘while on-treatment’ strategy for IE, as described in [Table 1](#).

If a participant takes an incorrect dose or miss a dose, PK concentrations and PK parameters inferred until the next dose (in case more than one dose is administered during the monotherapy period) or until the end of monotherapy period (if there is only one dose or if incorrect dose is the last one) may be excluded from PK data summaries, as instructed by CPMS prior to final database lock.

The following figures will be produced:

- A by-participant graph of concentration data over time, on linear and semi-logarithmic scales
- Graph of geometric mean of concentration data over time, on linear and semi-logarithmic scales
- Individual and box plot of PK parameters

Listings of PK concentration and PK parameter values will be produced.

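### The SAP derives VH4011499 PK parameters only from data up to discontinuation, so a participant who misses the Day 6 dose always loses C11 and has AUC0-11 truncated, although the samples are taken

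*SAP*

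**What the plan says.** SAP 1.2 gives VH4011499 on Days 1 and 6. Protocol 7.1 counts anyone who has not received all planned doses as having discontinued, and keeps that person in the study on the normal visit schedule. The schedule of activities takes plasma PK at every visit from Day 1 to Day 39.

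The data after discontinuation are then handled in two ways.

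- **HIV-1 RNA (primary estimand, SAP 1.1.1):** treatment policy; "any HIV-1 RNA data available after study treatment discontinuation day + 1 and prior to starting SoC will be used in calculation of max VLD". The safety estimand also uses treatment policy for discontinuation.
- **VH4011499 concentrations (PK estimand, SAP 1.1.1):** while on-treatment; "concentration values after study treatment discontinuation day + 1 will be excluded from analysis". The stated reason is that discontinuation may bias the description of PK behaviour over the 10-day period.

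SAP 4.3.2.3 carries the PK rule into derivation: "only serum concentration data up to the time of discontinuation of VH4011499 will be used in derivation of VH4011499 PK parameters". It repeats the rule for summaries without the extra day: "PK concentrations derived after discontinuation of study treatment will be excluded from PK data summaries". SAP 4.6.2 excludes post-discontinuation parameters from other PK statistical analyses.

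The parameters in SAP Table 3 include C11 ("Concentration on Day 11") and AUC0-11. SAP 4.3.2.3 leaves AUC0-11 out of the descriptive summaries and reserves it for relating exposure to safety and immunologic endpoints. Protocol 9.4.3.3 describes exposure-response as "The relationship between selected PK parameters (e.g., concentrations on Day 11) and selected PD parameters", with no imputation, and defers the details to a CPMS analysis plan. SAP 4.3.2.5 likewise leaves the relationship with viral load decline to CPMS.

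**The concern.** Describing the PK of a planned regimen and relating exposure to outcome are different questions. For the first, leaving out concentrations after a missed dose is reasonable. For the second, the concentration actually present is the relevant predictor, whether or not the Day 6 dose was given. The SAP writes its cut into the derivation of the parameters, so it reaches both uses unless something else overrides it.

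Two things are at stake. First, a participant stopped for safety, for example on the liver chemistry criterion in Protocol 7.1.1, is the one whose exposure matters most in an exposure-safety plot. That person would have a missing or understated AUC0-11. Second, Protocol 4.3 describes planned exposures as "aimed to characterize the near maximal decline in HIV-1 RNA", so a participant who received only the first dose could supply an informative lower-exposure point.

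**Working it through.** **1. Is Day 11 always past the cut-off?** Under Table 1 the last retained day is d + 1, where d is the discontinuation day. Day 11 is excluded when 11 > d + 1, that is, for every d from 1 to 9. A participant who misses the Day 6 dose is dated no earlier than Day 1 (last dose) and no later than Day 6 (missed dose). C11 is therefore excluded in every case, and under the earlier cut in 4.3.2.3 as well.

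**2. How much of the profile is lost?** There are seven PK visits in the schedule through Day 11: Days 1, 2, 3–5, 6, 7, 8–10 and 11.

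| Discontinuation dated | Last day kept, Table 1 (d + 1) | Visits lost | Last day kept, 4.3.2.3 (d) | Visits lost |
|---|---|---|---|---|
| Day 1 | Day 2 | 5 of 7 | Day 1 | 6 of 7 |
| Day 6 | Day 7 | 2 of 7 | Day 6 | 3 of 7 |

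The legible text does not fix the date, and the two sections differ by a day for either date. AUC0-11 stops at the cut in all four cells. The SAP does not say whether the partial area is then reported or set to missing.

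**3. What survives?** At day level, the Day 1 samples fall before either cut-off. Cmax and tmax from those samples remain and can be paired with maximum viral load decline. They carry no information about omission of the Day 6 dose.

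**4. How likely is a case?** The documents give no discontinuation rate, so p is assumed. The chance of at least one case among n active participants is 1 − (1 − p)^n. Part 1b has 6 + 6 = 12 active; Part 2b adds 6 if it is run with two doses.

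| p | n = 12 | Expected number, 12p | n = 18 |
|---|---|---|---|
| 2% | 1 − 0.98^12 = 22% | 0.24 | 30% |
| 5% | 1 − 0.95^12 = 46% | 0.60 | 60% |
| 10% | 1 − 0.90^12 = 72% | 1.20 | 85% |

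One case is 1 of 6 (17%) in an arm.

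**5. What could one case be worth in an exposure-response plot?** The measure is the share of the sum of squares of log exposure lost when that participant is dropped. The simulation (20,000 runs) has 6 participants at 25 mg and 6 at 100 mg (doses from SAP 1.2), exposure proportional to dose and a log-SD of 0.3. The last two, and the fold-reductions below, are assumptions.

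| Stopper's C11 lower by | Stopper in 25 mg arm | Stopper in 100 mg arm |
|---|---|---|
| 2-fold | 25% | 1.5% |
| 4-fold | 41% | 7% |
| 8-fold | 55% | 22% |

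Dropping an ordinary participant costs about 9%. The loss can be large or trivial, depending on who stops.

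**The case against.** A reader might infer that early stoppers cannot contribute to the exposure-response objective at all. The documents do not support that.

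- The exclusion is stated under the PK-profile objective. Exposure-response with viral load belongs to a CPMS plan that is not among the documents, and nothing legible says the exclusion carries over. Protocol 9.4.3.2 also allows a separately reported population PK analysis.
- The endpoint is PK parameters in the plural, and Day 11 concentration is only an example. Day 1 Cmax and tmax still pair with maximum viral load decline.
- SAP 4.6.3 and 4.6.4, where AUC0-11 is to be used, are redacted, as are some estimand rows and part of the intercurrent-event text in Protocol 9.4.3.2. An overriding rule could stand there.
- Different strategies for different objectives are not in themselves an error, and the PK strategy has a stated reason.
- For a missed dose, SAP 4.3.2.3 and 4.6.2 make exclusion discretionary, in 4.3.2.3 on CPMS instruction.
- Non-safety stoppers may be replaced, and the exposure-response analysis is exploratory.

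All of this limits the point without removing it. SAP 4.3.2.3 is legible and sets how the parameters are derived for the final datasets; without a contrary statement, those are the natural input to later analyses. The discretionary missed-dose rule does not settle the matter, because under Protocol 7.1 a missed Day 6 dose is also a discontinuation, for which the exclusion is mandatory. Replacement is barred for attributable safety stops, the cases of most interest for exposure-safety.

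**Conclusion.** The point holds within limits. Under the legible derivation rule, a VH4011499 participant who does not receive the Day 6 dose always loses C11 and has AUC0-11 truncated, although the samples are collected and the outcome data are kept. The effect on AUC0-11 is direct, subject to whatever the redacted sections say. The effect on C11 against maximum viral load decline is conditional on CPMS using the SAP-derived parameters. Separately, the cut-off is worded inconsistently within the SAP, and this needs correcting whatever the CPMS plan says.

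The scope is narrow. VH4004280, given once, is untouched, as would be a Part 2b regimen given only on Day 1. Perhaps no participant or one will be affected: the 22%, 46% and 72% chances rest on assumed rates. The larger figures, 25–55% of exposure spread and 5 of 7 visits, should not be read as the expected loss. The first needs a low-dose stopper with a marked fall in concentration; the second needs discontinuation dated to Day 1. A high-dose stopper gives about 1.5–22%, and dating to Day 6 loses 2 of 7 visits under Table 1. The primary analysis is not affected.

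**What to change.** - Keep the while-on-treatment exclusion for descriptive PK summaries by planned regimen. Use one cut-off in SAP Table 1, the derivation text and the summary text of 4.3.2.3, and state how the discontinuation day is dated when the Day 6 dose is not given.
- State in SAP 4.3.2.3 and 4.6.2, and carry into the CPMS plan, that C11 and AUC0-11 for exposure-response and exposure-safety analyses are derived from all concentrations measured before standard of care starts, using actual dosing history.
- Flag part-regimen participants in those analyses.

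The cost is wording in the SAP and the CPMS plan, plus a second derivation of two parameters for any affected participant. No visit, sample or assay is added. The small downside is that these analyses mix full- and part-regimen participants, which the flag makes visible.

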1.2. Study Design

Overview of Study Design and Key Features	
	
Design Features	
 Phase IIa, PoC, multi-center, randomized, double-blind (sponsor unblinded), placebo-controlled (by each capsid inhibitor) study Orally administered VH4004280 and VH4011499 monotherapy over 10 days in ART naive HIV-1 viremic adults The study will evaluate the antiviral effect, safety, tolerability and PK/PD of VH4004280 and VH4011499 Participants have a Screening visit approximately 7 to 14 days prior to first dose on Day 1 On Day 1 randomized participants enter a monotherapy phase of 10 days (i.e. up to Day 11) On Day 11, after collection of HIV-1 RNA sample, participants will start open-label SoC combination ART CCI Total duration of study participation is approximately 45 to 66 days based on the following: 
 7 to 14 days, with a maximum of 28 days permitted in some cases for screening/qualification period, 10 days for treatment with the study intervention (monotherapy period) and 28 days for follow up visits (Follow-Up period)
Study intervention	
 A single dose of orally administered VH4004280 or matched placebo for VH4004280 on Day 1 or

Overview of Study Design and Key Features	
	
 • A single dose of orally administered VH4011499 or matched placebo for VH4011499 on Days 1 and 6
Study intervention Assignment	
 • Part 1a: 100mg VH4004280, 300mg VH4004280 or placebo in a 6:6:2 ratio • Part 2a (if conducted): 50-600mg VH4004280 (exact dose to be decided after first Interim) or placebo in a 6:1 ratio • Part 1b: 25mg VH4011499, 100mg VH4011499 or placebo in a 6:6:2 ratio • Part 2b (if conducted): 100mg on Day 1 to 250mg on Days 1 & 6 VH4011499 (exact dose to be decided after second Interim) or placebo in a 6:1 ratio
Interim Analysis	
 • A first informal interim analysis will be conducted after 9 participants (i.e., 4 participants per active arm and 1 placebo participant) from Part 1a have completed their Day 11 visit. • A second informal interim analysis will be conducted after 9 participants (i.e., 4 participants per active arm and 1 placebo participant) from Part 1b have completed their Day 11 visit. • Conduct of parts 2a and 2b depend on results of first and second interim analysis, respectively

2. STATISTICAL HYPOTHESES

The primary objective will be addressed using an estimation approach (descriptive statistics) with no hypothesis testing. The primary treatment effect to be estimated is the maximum change from Baseline in plasma HIV-1 RNA over the monotherapy period for each dose for both VH4004280 and VH4011499 CAIs.

2.1. Multiplicity Adjustment

No adjustment for multiplicity will be made.

3. ANALYSIS SETS

Analysis Set	Definition	Analyses Evaluated
Screened	
 • All participants who are screened for eligibility 	Study Population

Analysis Set	Definition	Analyses Evaluated
Randomized	
 All participants who are randomly assigned to study treatment (i.e., VH4004280, VH4011499 or placebo) in the study 	Study Population
Safety	
 All randomized participants who take at least 1 incorrect or correct dose of study treatment Participants will be analyzed according to the treatment they actually received 	Study Population, Safety
Full Analysis Set (FAS)	
 All randomized participants who received at least one correct dose of study treatment Data will be reported according to the randomized study intervention 	Efficacy, Study Population
Per-Protocol (PP)	
 All participants in the full analysis set for whom there were no major protocol deviations that impact the primary analyses Data will be reported according to the treatment actually received Specific details of major protocol deviations that would exclude participants from the PP analysis set are provided in Section 3.1 	Efficacy The PP set will not be used for an analysis if it is the same as FAS
Pharmacokinetic (PK)	
 All participants in the Safety analysis set who had at least 1 non-missing PK assessment (Non-quantifiable [NQ] values will be considered as non-missing values) Data will be reported according to the actual study treatment 	PK

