• Maximum change from baseline (Day 1) in plasma HIV-1 ribonucleic acid (RNA) through Day 11.	Overtly healthy (other than HIV-1 infection) treatment naïve individuals	VH4004280 or placebo single dose on Day 1 or VH4011499 or placebo single dose on Day 1 and Day 6	Mean of maximum change from Baseline in log10 HIV-1 RNA during Days 1-11	
Discontinuation of study treatment due to any reason: Treatment policy strategy, i.e., any HIV-1 RNA data available after study treatment discontinuation day + 1 and prior to starting SOC will be used in calculation of max VLD
 
Use of SOC medication prior to Day 11: While on-treatment strategy, i.e., HIV-1 RNA collected after initiation of SoC, if for any reason this takes place prior to Day 11 will be excluded from calculation of max VLD
 
Use of prohibited medication: Treatment policy strategy, i.e., any HIV-1 RNA data available after use of prohibited medication will be used in calculation of max VLD
 
Missed or partial doses of study treatment: Treatment policy strategy, i.e., HIV-1 RNA collected after missed or partial dose(s) will be used in calculation of max VLD
 
Rationale: Interest is in evaluating efficacy irrespective of study treatment discontinuation or missed/partial doses, or use of prohibited medications, hence a treatment policy strategy is appropriate. Also, interest is to evaluate efficacy of VH4004280/VH4011499 monotherapy and not in combination with other antiretroviral medication hence a while on-treatment strategy is appropriate.
 
Note: discontinuation or missed or partial doses of VH4004280 is not possible as only a single dose on Day 1 is administered, hence these IEs apply only to VH4011499 and to placebo matched for VH4011499.

Secondary Objective: To assess the safety and tolerability of orally administered VH4004280 and VH4011499				

Endpoints	Estimand			
	Population	Treatment	Summary Measure	Intercurrent event (IE) / strategy / rationale

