4.6.2. Other Pharmacokinetic Analyses

All other pharmacokinetic analyses will be performed on the Pharmacokinetic analysis set.

For other pharmacokinetic statistical analyses:

- If any PK parameters are derived after discontinuation of study treatment, these will be excluded from statistical analyses in accordance with the “while on-treatment” strategy for IE as described in [Table 1](#).
- If a participant takes an incorrect dose or miss a dose, PK parameters inferred until the next dose (in case more than one dose is administered during the monotherapy period) or until the end of monotherapy period (if there is only one dose or if incorrect dose is the last one) may be excluded from the statistical analyses, as appropriate.

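### In single-dose regimens the SAP's full analysis set drops anyone given a wrong amount, although the primary estimand declares interest in efficacy irrespective of incorrect doses

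*SAP*

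**What the plan says.** The primary efficacy analysis runs on the FAS (SAP 4.2.2). SAP Section 3 defines that set as "All randomized participants who received at least one correct dose of study treatment", reported as randomised. The Safety set in the same table admits correct and incorrect doses alike. SAP 4.9 explains that the protocol's term for a partial dose was replaced by incorrect because an administration can turn out lower or higher than planned. It adds that the planned analyses are unaffected.

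For the primary estimand, SAP Table 1 applies a treatment policy strategy to this event: "HIV-1 RNA collected after missed or incorrect dose(s) will be used in calculation of max VLD". The rationale is "Interest is in evaluating efficacy irrespective of study treatment discontinuation or missed/incorrect doses, or use of prohibited medications".

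A note under the estimand says that "discontinuation or missed doses of VH4004280 is not possible as only a single dose on Day 1 is administered", and closes with "hence these IEs apply only to VH4011499 and to placebo matched for VH4011499". The protocol's version of the note named one more event: "discontinuation or missed or partial doses of VH4004280 is not possible as only a single dose on Day 1 is administered".

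SAP 1.2 gives VH4004280 and its placebo as one dose on Day 1. The range left open for Part 2b of VH4011499 includes a Day 1-only option.

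**The concern.** With a single administration, one wrong amount means no correct dose at all, so the FAS rule removes the participant. The estimand attached to that same analysis says such participants' viral load data are wanted. This is an exclusion after randomisation, based on dosing, in an analysis reported as randomised.

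The arms hold about six participants, so one removal is visible in the headline mean. The per-protocol (PP) set cannot reveal the effect. It is a subset of the FAS, and its exclusion 02 (any incorrect dose) finds nobody left to remove in a single-dose regimen.

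**Working it through.** The plan gives no figure to reproduce here: the sample size rests on feasibility and the precision table is redacted. The main check sets the provisions side by side.

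**Who is dropped**

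| Situation | FAS (SAP 3) | Primary estimand (SAP Table 1) |
|---|---|---|
| Single dose, correct | in | in |
| Single dose, lower or higher than planned | out | data used, if the event applies to this compound |
| Two doses, one correct and one incorrect | in | data used |
| Two doses, neither correct | out | data used |

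The rows conflict wherever there is no correct dose. The single-dose schedule covers 6 + 6 + 2 = 14 participants in Part 1a and 6 + 1 = 7 in Part 2a, so up to 21. Up to 7 more would join if Part 2b used a Day 1-only regimen, which is undecided.

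**Does the SAP foresee the case?** Yes. Section 4.3.2.3 allows PK data after an incorrect dose to be left out of summaries until the next dose or "until the end of monotherapy period (if there is only one dose or if incorrect dose is the last one". Section 4.6.2 repeats the rule for the PK models. The SAP note also no longer lists partial doses among the events that cannot occur with VH4004280.

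**Does the SAP change membership relative to the protocol?** Protocol 9.3 required at least one full dose, so a partial single dose was already excluded. A participant given more than planned could be taken to have had a full dose. Under the SAP wording that participant has no correct dose and is out. FAS membership can therefore change.

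**Does another planned analysis fill the gap?** SAP 4.2.3 and 4.2.4.1 repeat the analyses on the Safety set if someone receives a treatment other than the one randomised. Arms are defined by dose level, so receiving another arm's dose would probably trigger this. For an amount matching no arm, the text does not say. In either case the Safety set is analysed by treatment received, not as randomised. Replacement (SAP 4.1.1) covers early discontinuation, not incorrect dosing.

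**Size, for illustration.** Let d be the difference between the excluded participant's maximum decline and the mean of the other five. The documents give no value, so d is assumed. Including that participant shifts the arm mean by d/6:

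- d = 0.5: 0.5/6 = 0.08 log10
- d = 1.0: 1.0/6 = 0.17 log10
- d = 1.5: 1.5/6 = 0.25 log10

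**Precision.** With s5 the SD of the other five and s6 the SD of all six, s6² = (4·s5² + (5/6)·d²)/5 = 0.8·s5² + d²/6. The 95% interval at n = 6 is narrower than at n = 5 only if s6²/s5² < (2.776²/5)/(2.571²/6) = 1.40. That means d²/s5² < 6 × (1.40 − 0.8) = 3.6, or d below about 1.9·s5. Exclusion can therefore widen or narrow the interval, and no general claim about width is made.

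**Frequency.** No dosing-error rate is given. If it were 1% to 5% per participant (an assumption), the chance of at least one error, 1 − (1 − p)^n, would be 6% to 26% in an arm of 6 and 19% to 66% among 21.

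**The case against.** The best counter-argument is the note's closing clause. Table 1 lists missed and incorrect doses as one event. If the clause limits that whole event to VH4011499, the estimand never promised anything about incorrect doses of VH4004280, and FAS and estimand do not collide. The note is indeed unclear. This reading still does not rescue the plan: the note names only discontinuation and missed doses, the PK rules provide for an incorrect single dose, and the estimand's population is not restricted by dosing. Even on this reading, the estimand is silent for VH4004280 and participants are excluded without a stated reason.

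Other points carry some weight:

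- All HIV-1 RNA data go into a listing (SAP 4.2.2), so in a small descriptive study a reader could recompute the mean. That is a fair mitigation, but a listing is not the primary analysis.
- In a single-dose regimen the error happens on Day 1, before any post-baseline viral load exists, so it is not driven by response. This stands, and the point here is not that the exclusion is outcome-driven.
- Including the participant places someone who took another amount under the randomised dose level, in a study meant to describe dose-specific effect. This is a real cost, although it is what a treatment policy strategy reported as randomised implies, and the PP set then gives the result without them.
- A second staff member confirms each dose (Protocol 6.5), so the likeliest number affected is probably zero. This also stands.
- The criticism of SAP 4.9 depends on reading a higher-than-planned dose as a full dose, which the protocol does not settle. For that reason the claim is only that membership can change.

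**Conclusion.** The concern holds. For a single-dose participant given a wrong amount, the FAS rule and the primary estimand's declared interest give opposite answers, and no planned analysis set shows the as-randomised result with that participant included. In two-dose regimens only a participant with no correct dose is affected.

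The consequence is conditional on a rare event. One occurrence removes 1 of 6 (17%) in an active arm or 1 of 2 in the Part 1a placebo arm. The shift of 0.08 to 0.25 log10 in the active-arm mean rests on the assumed differences. The inconsistency itself rests on the text alone. It should be fixed before database lock, because the sponsor is unblinded and it is better not to settle who counts in an arm of six after the results are known.

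**What to change.** 1. In SAP Section 3, define the FAS as all randomised participants who took any study treatment, whether the dose was correct or incorrect, reported as randomised. PP exclusion 02 then does the removal, and comparing FAS with PP becomes informative about incorrect doses.
2. In the Table 1 note, state that the incorrect-dose event applies to VH4004280 and its placebo.
3. In Section 4.2.3, state whether a wrong amount of the assigned drug triggers the Safety-set repeat.
4. In Section 4.9, acknowledge that moving from full to correct can change FAS membership for a participant given more than planned.

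If the sponsor prefers to keep the FAS as written, the estimand should state the exclusion and its reason before database lock.

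The cost is one changed line and three clarifying sentences, with no extra data or participants. The analytic price is that a rare wrong-amount participant is counted under the randomised dose level in the primary table.
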